5.5 Treatment Period

5.5.1Study Procedures: Days -23 \pm 2; Days -16 \pm 2; Days -9 \pm 2; Days -2 \pm 2

- Physical/neurological examination
- Vital signs pre-treatment and one hour post-treatment
- Interval medical history
- KPS
- Review of concurrent medications
- Adverse event assessment
- Complete blood count (CBC) with differential and platelet count
- Blood chemistry assessment, including:
 - Alkaline phosphatase, aspartate aminotransferase/alanine aminotransferase (ALT/AST), total bilirubin, calcium, blood urea nitrogen (BUN), creatinine, total protein, albumin, random glucose, potassium, sodium, chloride, bicarbonate
- Vaccination with IMA-950 plus poly-ICLC (one formulation)
- Varlilumab (Arm 1 patients only) on Day -23 ± 2

- Collection of 8 x 10cc green top tubes and 1 x 5cc red top tubes for research blood samples on Day -23 ± 2
- (Arm 1 patients only) on the day of Varlilumab infusion (Day-23 ± 2), PK samples (1 x 10 cc red top tube/draw) should be drawn from the arm contralateral to the infusion site prior to administration and at 30 minutes (±5 minutes) after the end of the varlilumab infusion. An additional sample should be drawn as soon as possible for any patients who experience an infusion reaction.
- Assessment of vaccine injection site 48±6 hours post-injection which can be done
 either by phone or in person. Following Day -2 administration, the follow-up
 assessment will be on the day of surgery. The PI or a clinical co-investigator
 should visit the patient in the ward and make the assessments.

5.5.2Study Procedures, Day 0 (Surgical date)

- Pre-operative MRI per institutional standard of care (with a window of -2 days)
- Intraoperative collection of ≥ 0.5 grams of tumor tissue, snap frozen
- Intraoperative collection of 8 x 10cc green top tubes and 1 x 5cc red top tubes for research blood samples

5.5.3Study Procedure, Post-Op, within 14 ± 2 days of surgery

- Post-operative MRI
- Final pathology confirmation of WHO grade 2 glioma
- Review of expected date off of dexamethasone
- Vital signs
- Interval medical history
- KPS
- Review of concurrent medications
- Adverse event assessment
- Complete blood count (CBC) with differential and platelet count
- Blood chemistry assessment, including:
- Alkaline phosphatase, aspartate aminotransferase/alanine aminotransferase (ALT/AST), total bilirubin, calcium, blood urea nitrogen (BUN), creatinine, total protein, albumin, random glucose, potassium, sodium, chloride, bicarbonate

5.5.4Study Procedures Week A1 (≥ 2 weeks after post-op steroids are tapered off and ≤ 10 weeks post-operatively)

These procedures must be completed ≤ 7 days to A1, unless otherwise noted.

- Patient should meet all prior eligibility criteria
- Physical/neurological examination
- Vital signs (pre-treatment and one hour post-treatment)
- Interval medical history

- KPS
- Review of concurrent medications
- Adverse event assessment
- Vaccination with IMA-950 plus poly-ICLC (one formulation)
- Varlilumab infusion (Arm 1 patients only)
- Complete blood count (CBC) with differential and platelet count
- Blood chemistry assessment, including: Alkaline phosphatase, aspartate aminotransferase/alanine aminotransferase (ALT/AST), total bilirubin, calcium, blood urea nitrogen (BUN), creatinine, total protein, albumin, random glucose, potassium, sodium, chloride, bicarbonate
- Collection of 8 x 10cc green top tubes and 1 x 5cc red top tubes for research blood samples
- (Arm 1 patients only), PK samples (1 x 10 cc red top tube/draw) should be drawn from the arm contralateral to the infusion site prior to administration and at 30 minutes (±5 minutes) after the end of the varlilumab infusion. An additional sample should be drawn as soon as possible for any patients who experience an infusion reaction.
- Assessment of vaccine injection site 48±6 hours post-injection which can be done either by phone or in person

5.5.5Study Procedures Week A4 - A22

These procedures must be completed every 3 weeks (± 7 days)

- Physical/neurological examination
 - Vital signs (pre-treatment and one hour post-treatment)
- Interval medical history
- KPS
- Review of concurrent medications
- Adverse event assessment
- Vaccination with IMA-950 plus poly-ICLC (one formulation)
- Complete blood count (CBC) with differential and platelet count
- Blood chemistry assessment, including:
- Alkaline phosphatase, aspartate aminotransferase/alanine aminotransferase (ALT/AST), total bilirubin, calcium, blood urea nitrogen (BUN), creatinine, total protein, albumin, random glucose, potassium, sodium, chloride, bicarbonate
- Varlilumab infusion (Arm 1 patients only) on Weeks A7, A13 and A19
- Collection of 8 x 10cc green top tubes and 1 x 5cc red top tubes for research blood samples on Weeks A13 and A19
- (Arm 1 patients only) on the day of Varlilumab infusion (Weeks A7, A13 and A19), PK samples (1 x 10 cc red top tube/draw) should be drawn from the arm contralateral to the infusion site prior to administration and at 30

minutes (±5 minutes) after the end of the varlilumab infusion. An additional sample should be drawn as soon as possible for any patients who experience an infusion reaction.

- MRI scan on Weeks A10
- Assessment of vaccine injection site 48±6 hours post-injection which can be done either by phone or in person

5.5.6Study Procedures Week A25

These procedures must be completed ± 7 days

- Physical/neurological examination
- Vital signs
- Interval medical history
- KPS
- Review of concurrent medications
- Adverse event assessment
- Complete blood count (CBC) with differential and platelet count
- Blood chemistry assessment, including:
- Alkaline phosphatase, aspartate aminotransferase/alanine aminotransferase (ALT/AST), total bilirubin, calcium, blood urea nitrogen (BUN), creatinine, total protein, albumin, random glucose, potassium, sodium, chloride, bicarbonate
- Collection of 8 x 10cc green top tubes and 1 x 5cc red top tubes for research blood samples
- MRI scan
- ECG (if clinically indicated)

5.5.7 48 Hour Post-Vaccine Follow-up

Skin reactions secondary to the vaccine administration may lead to unique skin toxicity. Furthermore, the regime may cause systemic adverse events. Hence, observations for severe local and systemic reactions will be important. Patients will have follow-up at 48 ± 6 hours after each vaccine for adverse events. This may be by telephone assessment or in person.

If 48 ± 6 hours post-vaccine assessment is by telephone, the patient/parent/guardian will use the Vaccination Toxicity Assessment Form (Appendix III) to permit an accurate and consistent assessment of vaccine site reactions. Any telephone reported reactions consistent with ≥ Grade 3 should be followed by a clinic visit and appropriate management. Such a visit would ideally be with the primary research team and accomplished within 24-72 hours; however, if the patient is unable to travel to UCSF, then appropriate local referral will be facilitated (e.g., Dermatology, etc.).

12 April 2020 Page 36 of 88 confidential

Any telephone reported reactions \leq Grade 2 should be followed by another phone call approximately 48 hours later (96 \pm 6 hours post-vaccine). If telephone reported reaction at 96 \pm 6 hours post-vaccine is still \leq Grade 2 or improving, no further follow-up is necessary. However, if telephone reported reaction at 96 \pm 6 hours is \geq Grade 3 or worsening, the patient should be evaluated in person by a member of the research team. If the patient is unable to travel to UCSF, then appropriate local referral will be facilitated (e.g., Dermatology, etc.).

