7.1.3 Tumor Tissue Collection

In the operation room, at the time of surgical resection, after adequate tissue is provided to UCSF Medical Center Pathology for diagnosis, the request is made that approximately 0.3 grams of remaining viable tumor tissue is acquired and divided as follows by the Brain Tumor Research Center Tissue Bank.

- 1. 300 mg tumor tissue is snap frozen and collected for banking
- 2. 200 mg tumor tissue will be kept fresh and used for flow cytometric analysis of tumor-infiltrating leukocytes (TILs)

Note: A patient must have at least 200 mg tumor tissue available for TIL to remain eligible for the study.

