8.4 Evaluation of Tumor Infiltrating Leukocytes (TILs)

We will evaluate TILs in tumor tissues obtained from patients who received pre-surgical treatment with the IMA950+poly-ICLC vaccine with or without varillumab.

We will isolate TILs and evaluate whether surgically resected tumors from Arm 1 (IMA950+poly-ICLC vaccine **with** varlilumab) patients demonstrate significantly higher levels of vaccine-reactive T-cells and CXCL10 expression compared with:1) those resected from Arm 2 (IMA950+poly-ICLC vaccine **without** varlilumab) patients; and 2) HLA-A2+ patients who underwent resection under IRB# 15-17078 vaccine study.

We will also compare T-cell clonotypes of TILs with those in post-vaccine PBMC. Specifically, we will determine whether T-cell clonotypes that are reactive to IMA950 peptides in PBMC are found in TILs. To this end, IMA950-specific multimer-positive T-cells in post vaccine PBMC will be sorted, and T-cell receptor β-chain usage in those populations will be determined. Then, we will evaluate whether those T-cell populations are increased in TILs obtained from Arm 1 patients compared with those obtained from Arm 2 (and IRB# 15-17078 vaccine study) patients. This method is expected to be more sensitive than traditional multimer-based analysis.

We will also perform multi-color flow cytometry to characterize infiltrating T-cells in terms of their number, phenotype, and reactivity to IMA950 peptides by 6-hr *in vitro* re-stimulation with IMA950 peptides followed by staining of cytoplasmic IFN-γ. These studies will allow us to evaluate whether vaccine-induced T-cells efficiently traffic to the brain tumor site and maintain their function and viability. We will also evaluate the number and phenotype of CD33+CD11b+HLA-DR-or dim immature myeloid cells (IMCs) and other myeloid cells (including CD33+CD11b+HLA-DR+ cells) in TILs. RT-PCR will be applied to evaluate the

12 April 2020 Page 62 of 88 confidential

expression of chemokines, such as CXCL10, and immuno-regulatory substances, such as arginase-1.

9 Measurement of Effect

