9.2.7 Evaluation of leukocyte phenotypes in PBMC samples

Using flow-cytometry, we will also evaluate the numbers of lymphocyte subsets such as immature myeloid cells, CD4+ T cells, CD4+/Foxp3+ regulatory T cells in TIL and PBMC in an exploratory manner. These plans (in this paragraph) are immunological evaluations; however, do not compose the primary endpoints due to their exploratory nature. We will evaluate expression of perforin/IFN-γ (function) and Annexin-V (an apoptotic cell marker) in CD4+ and CD8+ T-cells, CD33+CD11b+HLA-DR- or dim immature myeloid cells and other myeloid cells (including CD33+CD11b+HLA-DR+ cells) per milligram of tumor tissue. We will use RT-PCR to evaluate expression of arginase-1, ROS, and NOS in flow-sorted myeloid cells.

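### The Day 0 list in 5.5.2 has all collected tumour snap frozen, which contradicts the 200 mg fresh portion in 7.1.3, and the 7.1.3 split does not fit the amount it requests

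*Combined protocol and SAP*

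**What the plan says.** The tissue instructions sit in several places in the protocol.

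- **Section 5.5.2 (Day 0).** The only tissue step is "Intraoperative collection of ≥ 0.5 grams of tumor tissue, snap frozen". It mentions no fresh portion and does not refer to 7.1.3.
- **Section 7.1.3 (Tumor Tissue Collection).** The request in the operating room is that "approximately 0.3 grams of remaining viable tumor tissue is acquired". The tissue bank then divides it in two: "300 mg tumor tissue is snap frozen and collected for banking", and "200 mg tumor tissue will be kept fresh and used for flow cytometric analysis of tumor-infiltrating leukocytes (TILs"). A note adds: "A patient must have at least 200 mg tumor tissue available for TIL to remain eligible for the study".
- **Section 3.1.4.** The expected resection is at least 0.3 g. The synopsis inclusion list still has 0.5 g.
- **Study calendar (Section 6).** The tumour tissue row has a mark at surgery and no footnote on handling.

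The tumour assays are in Sections 8.4, 9.2.1, 9.2.2 and 9.2.7. Section 8.4 isolates TILs and plans a 6-hour "re-stimulation with IMA950 peptides followed by staining of cytoplasmic" IFN-γ, with the aim of showing that T-cells in the tumour stay functional and viable. Section 9.2.7 adds "Annexin-V (an apoptotic cell marker") and sorting of myeloid cells. CXCL10 is measured by RT-PCR, and TCR clonotypes are sequenced from genomic DNA.

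**The concern.** The visit list and the tissue section give incompatible handling instructions for the same specimen. The protocol itself assigns fresh tissue to TIL flow cytometry and frozen tissue to banking. Restimulation, apoptosis staining and cell sorting call for intact, living cells, which a snap-frozen block does not supply.

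The tumour is taken at one scheduled operation, and freezing cannot be undone. Two things are at stake for a patient handled by 5.5.2 alone:

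1. The flow-based exploratory readouts for that patient are lost.
2. The patient has no tissue for TIL and may fail the 7.1.3 note. Section 5.5.4 asks that patients still meet eligibility at Week A1, and Section 4.3 restricts evaluability for the immunological co-primary endpoint to study-eligible patients. Read strictly, a tissue-handling slip could therefore end a patient's participation after four pre-surgical vaccines. Section 4.3 replaces non-evaluable patients, so the cost would be extra recruitment rather than a direct loss of the planned 15 per arm.

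**Working it through.** This is a mass balance; no sample-size formula applies.

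**Inputs.** Section 5.5.2: at least 500 mg, all frozen. Section 7.1.3: 300 mg frozen, 200 mg fresh, about 300 mg requested, and 200 mg for TIL needed to stay eligible. Section 3.1.4: at least 300 mg expected.

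**Step 1, the 0.5 g figure.** Frozen + fresh = 300 + 200 = 500 mg. The amount in 5.5.2 equals the whole 7.1.3 split, but 5.5.2 labels all of it frozen.

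**Step 2, the 0.3 g figure.** The 7.1.3 portions need 500 mg against about 300 mg requested, a shortfall of 500 − 300 = 200 mg. The section does not fit its own total.

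**Step 3, what each reading leaves.** For a specimen of T mg:

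- 5.5.2 taken literally: fresh = max(0, T − 500)
- 7.1.3, frozen portion first: fresh = max(0, T − 300)
- Fresh portion first: fresh = 200, frozen = T − 200 (for T of at least 200)

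| Specimen T | 5.5.2 literal: fresh | 7.1.3 frozen first: fresh | Fresh first: fresh / frozen |
|---|---|---|---|
| 300 mg | 0 mg | 0 mg | 200 / 100 mg |
| 500 mg | 0 mg | 200 mg | 200 / 300 mg |

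With the frozen portion first, the 200 mg condition is met only if T − 300 ≥ 200, that is, T ≥ 500 mg. With the fresh portion first, it is met whenever T ≥ 200 mg.

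**Step 4, satisfying both sections as written.** 500 mg frozen + 200 mg fresh = 700 mg, which is 700 / 300 = 2.3 times the minimum expected in 3.1.4.

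**Step 5, which readouts depend on fresh tissue.**

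- *Dependent:* TIL isolation and counts, phenotype, 6-hour restimulation, Annexin-V, and RT-PCR on flow-sorted myeloid cells.
- *Not tied by the documents to fresh tumour:* CXCL10 RT-PCR and TCR sequencing. For the latter, the reference clones are sorted from post-vaccine PBMC and the tumour contributes genomic DNA.
- *Not dependent on tumour at all:* the co-primary multimer assay, which uses PBMC.

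**The case against.** The strongest reply is that 7.1.3, not 5.5.2, governs. It is the section addressed to the operating room, it names the tissue bank that divides the specimen, and its eligibility note sends anyone checking eligibility back to it. There is one site, so staff may already handle tissue correctly. Section 5.5.2 is a short checklist, and its amount is a minimum that does not forbid a further fresh piece. The affected readouts are exploratory, and Section 9.2 says such data will be tabulated because the study is not powered for them. Section 9.2.2 already foresees too few TILs for reliable flow data and plans sequencing as a more sensitive route.

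Most of this stands, and it lowers both the likelihood and the weight of the problem. It does not remove it. Section 7.1.3 states no order of priority, lists the frozen portion first, and cannot be met at the amount it requests. Deferring to 7.1.3 can therefore end with the same 0 mg fresh. A further fresh piece on top of 5.5.2 needs 700 mg.

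Two stronger readings are tempting. A reader might infer that the trial has no fresh-tissue plan and will obtain no TIL data. The documents do not support that, because 7.1.3 provides the fresh portion and the loss arises only where it is not followed or its frozen part is taken first. A reader might also infer that the flow readouts are the reason for vaccinating before surgery. Section 2.8 gives a broader reason, evaluating vaccine effects in the tumour microenvironment, which CXCL10 expression and TCR clonotypes also serve.

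**Conclusion.** This is a document inconsistency in the current text, not a flaw in the design, and it should be corrected. Section 5.5.2 contradicts 7.1.3 on handling, and 7.1.3 contradicts itself on amount by 200 mg.

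The size is per patient and conditional. Where 5.5.2 is followed, or where 300 mg is frozen first from a 0.3 g specimen, 0 mg is left fresh against the 200 mg required, and the exploratory flow-based TIL readouts are lost for that patient. Eligibility under the 7.1.3 note may be lost too. The documents give no basis for estimating how often this would happen.

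The conclusion assumes that snap-frozen tissue does not yield cells fit for restimulation, Annexin-V staining or sorting, which agrees with the protocol's own assignment of fresh tissue to TIL flow cytometry. It also assumes that the 7.1.3 note is applied as written.

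**What to change.** Use one instruction on both handling and amount, and carry it through 5.5.2, 7.1.3, 3.1.4 and the calendar tissue row:

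- After diagnostic tissue is secured, set aside the 200 mg fresh TIL portion first, then snap freeze the remainder for banking (about 100 mg from a 0.3 g specimen, 300 mg from 0.5 g).
- In 7.1.3, replace the fixed 300 mg frozen portion with the remainder, so that the parts fit the total.
- Replace the 5.5.2 bullet with this instruction, and add a footnote to the calendar row that points to 7.1.3.
- State one expected amount throughout, including the synopsis line that still has 0.5 g.

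Fresh-first is an inference from the 200 mg eligibility note, since 7.1.3 gives no order, so the sponsor should confirm it with the tissue bank. Changing 5.5.2 alone, or only pointing it to the present 7.1.3, would not secure the fresh portion. The cost is a few lines of text and no new procedure. The small downside is less banked frozen tissue when the specimen is under 0.5 g.

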- Off or low dose (≤ 4 mg/day by Decadron) corticosteroid at least two weeks before the first pre-surgical vaccine
- Adequate organ function within 14 days of study registration including: 1)
 Adequate bone marrow reserve: absolute neutrophil (segmented and bands)
 count (ANC) ≥1.0 x 10⁹/L, absolute lymphocytes ≥400/µL, platelets ≥100 x
 10⁹/L; hemoglobin ≥ 8 g/dL; 2) Hepatic: Total bilirubin ≤ 1.5 x upper limit of
 normal (ULN) and SGPT (ALT) ≤ 2.5 x upper limit of normal (ULN), and 3)
 Renal: Normal serum creatinine or creatinine clearance ≥60 ml/min/1.73 m²
- Must be free of systemic infection. Subjects with active infections (whether or not they require antibiotic therapy) may be eligible after complete resolution of the infection. Subjects on antibiotic therapy must be off antibiotics for at least 7 days before beginning treatment.
- Sexually active females of child bearing potential must agree to use adequate contraception (diaphragm, birth control pills, injections, intrauterine device [IUD], surgical sterilization, subcutaneous implants, or abstinence, etc.) for the duration of the vaccination period. Sexually active males must agree to use barrier contraceptive for the duration of the vaccination period.
- Patient must sign an informed consent document indicating that they are aware
 of the investigational nature of this study, which includes an authorization for
 the release of their protected health information

Key Exclusion Criteria:

- Presence of gliomatosis cerebri, cranial or spinal leptomeningeal metastatic disease
- Presence of T1 Gadolinium (Gd) –enhancing lesions (on MRI) suggestive of high-grade glioma
- Pathological diagnosis for the resected tumor demonstrates transformation to higher grade (i.e. WHO grade III or IV) or gliomas. If a patient who received pre-surgical vaccines is diagnosed as high-grade glioma (HGG), the patient will be withdrawn from the study and considered for therapeutic options for HGG (trials for HGG or standard of care). The tumor tissue of such a case would be brought to the lab before the pathological diagnosis is made; and thus would be processed before the lab is informed of the final HGG diagnosis. Because HGG tissue may still reflect the vaccine effects, we will evaluate the tumor tissue to help us develop future approaches for HGG.
- Pregnant women are excluded from this study. Pregnancy testing will be performed on all menstruating females within 14 days prior to study enrollment

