- 3.1.10 Women of child-bearing potential and men must agree to use adequate contraception (ex. Hormonal or barrier method of birth control or abstinence) prior to study entry and for the duration of study participation (until one month after the last vaccine) since the effects of the current regimen on the developing human fetus are unknown. Should a woman become pregnant or suspect she is pregnant while she or her partner is participating in this study, she should inform her treating physician immediately.
- **3.1.11** Patient must sign an informed consent document indicating that they are aware of the investigational nature of this study, which includes an authorization for the release of their protected health information
- 3.2 Exclusion Criteria
- 3.2.1 Presence of gliomatosis cerebri, cranial or spinal leptomeningeal metastatic disease
- **3.2.2** Presence of T1 Gadolinium (Gd) –enhancing lesions (on MRI) suggestive of high-grade glioma
- 3.2.3 Pathological diagnosis for the resected tumor demonstrates transformation to higher grade (i.e. WHO grade III or IV) gliomas. If a patient is diagnosed as HGG upon resection after receiving the pre-surgical treatment, the patient will be withdrawn from the study and considered for therapeutic options for HGG (trials for HGG or standard of care). The tumor tissue of such a case would be brought to the lab before the pathological diagnosis is made; and thus would be processed before the lab is informed of the final HGG diagnosis. Because HGG tissue may still reflect the

12 April 2020 Page 25 of 88 confidential

- vaccine effects, we will evaluate the tumor tissue to help us develop future approaches for HGG.^{75,76}
- 3.2.4 Pregnant women are excluded from this study because IMA950 and poly-ICLC are drugs with the potential for teratogenic or abortifacient effects. Because there is an unknown but potential risk for adverse events in nursing infants secondary to treatment of the mother with IMA950 plus poly-ICLC (IMA950-poly-ICLC hereafter) vaccine, breastfeeding should be discontinued if the mother is treated with IMA950-poly-ICLC vaccine.
- 3.2.5 Uncontrolled intercurrent illness including, but not limited to ongoing or active infection (including active/chronic hepatitis B and C), symptomatic congestive heart failure, unstable angina pectoris, or psychiatric illness/social situations that would limit compliance with study requirements

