5.4 Screening

The screening procedures and assessments must be completed within 28 days or less of registration unless otherwise noted

- Informed consent
- Demographics
- Physical/neurological examination

12 April 2020 Page 32 of 88 confidential

- Vital signs
- Complete medical history
- KPS
- Review of concurrent medications
- MRI with and without contrast
- ECG
- UCSF pathology review for confirmation of WHO grade 2 glioma
- Complete blood count (CBC) with differential and platelet count
- Blood chemistry assessment, including:
 - Alkaline phosphatase, aspartate aminotransferase/alanine aminotransferase (ALT/AST), total bilirubin, calcium, blood urea nitrogen (BUN), creatinine, total protein, albumin, random glucose, potassium, sodium, chloride, bicarbonate
- Laboratory autoimmune assessment
 - Antinuclear antibody, thyroid-stimulating hormone (TSH), free thyroxine (FT4), rheumatoid factor
- Serum or urine pregnancy within 7 days prior to registration
- HBsAg, HBsAb and HBcAb for screening of active or chronic hepatitis B and C
- Urine analysis
- HLA typing prior to registration (must be positive for HLA-A2 based on flowcytometry or genotyping) *HLA typing can be done at any time prior to registration; 28 days or less of registration does not apply.

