• If the scheduled craniotomy is delayed for reasons not related to toxicities, i.e. related to surgical scheduling issues or patient preference, patients will still be eligible if surgery is performed ≤ 35 days from randomization AND ≤ 4 days from last vaccine.

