5.10 Duration of Therapy

In the absence of treatment delays due to AEs, treatment may continue Week 25 or until one of the following criteria applies:

- Rate limiting toxicity as defined above
- Disease progression
- Intercurrent illness that prevents further administration of treatment
- Patient decides to withdraw from the study
- Participant is noncompliant with the non-treatment requirements of the study
- Pregnancy. Pregnant participants will continue to be followed for the duration of the pregnancy.
- General or specific changes in the patient's condition render the patient unacceptable for further treatment in the judgment of the investigator

Patients removed from study for unacceptable AEs will be followed until resolution or stabilization of the adverse event. Patients who discontinue study treatment will be followed for survival according to the long term follow-up. Documentation of AEs and concomitant medications will continue during follow-up.

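### Pregnancy is tested only at screening, so the eligibility re-check at Week A1 rests on a result roughly 5 to 19 weeks old

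*Combined protocol and SAP*

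**What the plan says.** Section 3.2.4 gives the reason for the exclusion: "Pregnant women are excluded from this study because IMA950 and poly-ICLC are drugs with the potential for teratogenic or abortifacient effects". Section 3.1.10 covers the regimen as a whole. It states "Women of child-bearing potential and men must agree to use adequate contraception", gives as its reason "since the effects of the current regimen on the developing human fetus are unknown", and asks a woman who is or may be pregnant to tell her physician at once.

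The test at entry appears in two places with different windows. Section 5.4 has "Serum or urine pregnancy within 7 days prior to registration". The synopsis (Key Exclusion Criteria) has "Pregnancy testing will be performed on all menstruating females within 14 days prior to study enrollment".

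After entry, the first line of the Week A1 list in Section 5.5.4 is "Patient should meet all prior eligibility criteria", under a general rule that A1 procedures fall within 7 days of A1. Section 5.10 includes among the reasons for ending treatment "Pregnancy. Pregnant participants will continue to be followed for the duration of the pregnancy". The calendar in Section 6 marks B-HCG once, in the screening column.

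**The concern.** The plan treats pregnancy as a hazard at entry, asks for eligibility to hold again at A1, and stops treatment if pregnancy occurs. No scheduled procedure after screening would find one. Other criteria that can change over time do get a named re-check around A1: blood count, chemistry, performance status and concurrent medications in 5.5.4, and an MRI within 28 days before A1 in the calendar footnotes.

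What is at stake is participant safety, not any statistical figure. As the schedule stands, a woman could restart dosing after surgery on a result obtained before her first vaccine. The teratogenicity statement in 3.2.4 names only IMA950 and poly-ICLC; for varlilumab as part of the regimen, the plan says only that fetal effects are unknown.

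**Working it through.** The plan gives no figure for the age of the test at A1, so there is none to reproduce. The age follows from the visit windows.

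**Where a test is scheduled**

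- Section 5.4 (screening): yes.
- Sections 5.5.1 to 5.5.3 (pre-surgical visits, surgery, post-op): none listed.
- Section 5.5.4 (A1), 5.5.5 (A4 to A22), 5.5.6 (A25), 5.5.7 and 5.5.8 (follow-up): none listed.
- Calendar: one B-HCG mark, at screening. The neighbouring hepatitis and ECG rows each keep a second mark at A25, so a mark lost in text extraction is unlikely.

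**Inputs**

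- Test to registration or enrollment: 0 to 7 days (5.4) or 0 to 14 days (synopsis).
- Enrollment to randomization: 0 to 14 days (calendar footnote).
- First vaccine to surgery: 21 to 25 days (day -23 ± 2).
- Randomization to surgery, upper limit: 35 days. Section 5.7.1 keeps a patient eligible "if surgery is performed ≤ 35 days from randomization", with a further limit on the time since the last vaccine.
- Surgery to A1: at least 2 weeks after the steroid taper, at most 10 weeks (70 days).
- A1 to A22: 21 weeks (147 days).

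**Short end at A1.** Test, registration and first vaccine on the same day, surgery 21 days later, no post-operative steroid taper:

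0 + 21 + 14 = 35 days = 5 weeks.

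**Long end at A1**

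- Synopsis window: 14 + 14 + 35 + 70 = 133 days = 19 weeks.
- Section 5.4 window: 7 + 14 + 35 + 70 = 126 days = 18 weeks.
- Without the 14-day step from enrollment to randomization: 133 − 14 = 119 days (17 weeks) or 126 − 14 = 112 days (16 weeks).

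**At the last vaccine, A22**

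- Short end: 35 + 147 = 182 days = 26 weeks.
- Long end: 133 + 147 = 280 days = 40 weeks, or 126 + 147 = 273 days = 39 weeks under 5.4.

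**Treatment still to come at A1**

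- Vaccines: 4 before surgery and 8 after, so 8 of 12.
- Varlilumab in Arm 1: day -23, A1, A7, A13 and A19, so 4 of 5.

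**With a test inside the existing A1 window**

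- At A1: 0 to 7 days.
- At A22: 147 to 154 days (21 to 22 weeks).

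**The case against.** The strongest reply is that A1 already carries the duty. Non-pregnancy is an eligibility criterion, all criteria must hold at A1, and A1 procedures have a 7-day window, so a careful site would confirm it and only the method goes unnamed. That reading is open. But a general sentence does not put a test on the schedule, and the criteria that are re-tested around A1 are named individually.

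The residual risk is also narrow. Contraception is required until one month after the last vaccine, a suspected pregnancy must be reported at once, history and examination are repeated at every dosing visit, and a known pregnancy ends treatment. This stands, and it limits the weight of the point. What remains is an unrecognised pregnancy. The test age measures the gap in the schedule; it does not estimate how many women would be exposed.

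Other criteria, such as the autoimmune and thyroid tests, are likewise tested only at screening. That is true. Pregnancy is singled out because of the hazard that 3.2.4 states.

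The upper figure stacks maxima. It uses a footnote that gives no direction and a 35-day limit written for surgical delays not caused by toxicity. This is fair: 19 weeks is an outer bound, not a typical value. The conclusion needs only the short end.

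The 7-day against 14-day difference is minor. If registration and enrollment coincide, a test that meets 5.4 also meets the synopsis. It is a matter of tidying.

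Finally, an A1 test leaves the later doses without one. That is so; how often to repeat it is a judgement for the investigators.

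**Conclusion.** The concern holds. The only scheduled pregnancy test is at screening, and nothing scheduled supports the A1 re-check or the stop for pregnancy in 5.10. The result is at least 5 weeks old at A1 and up to about 18 or 19 weeks, depending on which entry window applies.

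The range assumes that registration and enrollment fall on the same date and that randomization follows enrollment. The 35-day limit does not fit the lead-in patients, who are assigned rather than randomized. Dosing delays of up to 6 weeks and the ± 7-day rescheduling windows are left out and could lengthen the interval. No limit from randomization to first dose is stated, so the age of the test at the first vaccine cannot be given.

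The existing safeguards keep this below an essential change. With a stated fetal hazard and so simple a remedy, it should still be made.

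**What to change.** - Add a serum or urine pregnancy test for women of child-bearing potential to the Week A1 list in 5.5.4 and to the B-HCG row of the calendar, within the existing 7-day window and with the result known before dosing.
- Use one entry window in both 5.4 and the synopsis, and tie it to the first dose as well as to registration.
- Leave to the investigators whether later dosing visits also need a test, and record the decision.

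The cost is wording in four places (calendar, 5.4, 5.5.4 and synopsis) and one or two inexpensive tests per woman of child-bearing potential, at visits where blood is already drawn. Sample size, endpoints and analyses do not change.
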